#### 4.3.2. Exclusion Criteria

- History of unsafe alcohol consumption
- Other liver disease (chronic viral/autoimmune/hereditary)
- Use of steatogenic medications
- History of drug dependence
- Body mass index (BMI) ≥35 kg/m2

28.02.2025

- A restrictive diet or weight change  $\geq 5$  kg during the 3 months prior to study
- Pregnancy or lactation
- Patients with sensitivity to caffeine intake
- Patients with symptomatic ischaemic heart disease, arrythmia's
- Any condition that, in the opinion of the clinician, would contraindicate the patient's participation.

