#### Laboratory investigations

Serum fasting plasma glucose, Lipid profile, Liver enzymes will be done to assess the
baseline fasting blood glucose for recruitment into the study to comply with inclusion
criteria. Serum HCG will be tested for female participants to exclude pregnancy.
Abdomen ultrasound scan will be performed to assess eligibility to the study.

28.02.2025

After recruitment baseline testing will be done for HbA1c, serum Insulin level, fasting
plasma glucose, Lipid profile, Liver enzymes. Serum creatinine, full blood count, serum
electrolytes and urine analysis will be done for safety assessments.

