### 5.4. Alcohol consumption

Intake of alcohol is not recommended and if consumed should not exceed the limit mentioned in exclusion criteria 20 g/day for women and 30g/day for men  $\geq 2$  units alcohol/day for women and  $\geq 3$  units for men during the study period.

The Alcohol Use Disorders Identification Test (AUDIT) is a 10-item screening tool developed by the World Health Organization (WHO) to assess alcohol consumption, drinking behaviors, and alcohol-related problems. This is validated questionnaire and Sinhala and Tamil translations are freely available to use. Frequency of alcohol consumption will be assessed monthly using AUDIT questionnaire in all patients.

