#### Criteria for stopping the trial or discontinuation of study intervention

28.02.2025

Individual subjects dosing will be stopped immediately if clinically relevant allergic reaction/ hypersensitivity occurs which needs medical intervention.

- 1. Dosing will be stopped if liver enzymes increases > 3 x normal range
- 2. Dosing will be stopped if conjugated bilirubin increases > 1.5 x normal range
- 3. Dosing will be stopped if serum creatinine increases > 1.5 x normal range
- 4. Dosing will be stopped if subjects suffer from a drug related (assessed as possibly or probably) and clinically relevant AE of moderate or severe intensity.
- 5. Any clinically significant values outside the reference ranges with major deviation and/or possible pathological relevance in physical examination, biochemical examination, hematology, vital signs measurements, electrocardiogram (ECG), and urinalysis.
- 6. Patients with AUDIT score > 8.

A volunteer can decide to withdraw from study participation at any time, for any reason, specified or unspecified, and without penalty or loss of benefits to which the subject is otherwise entitled. In this case, the subject must immediately contact the investigator and state that he is leaving the study.

Reasons for the withdrawal of the study (AE, ineffective treatment, inability to comply with the study requirements etc.) will be sought, if the patient is willing to provide that information. They will be made aware that their decision will in no way affect their treatment, and that they will be free to withdraw from study at any time. To respond to questions and record complaints during the study, contact details of two investigators will be provided to the study participants. Patient can be withdrawn from the study upon the principal investigator's decision to terminate the study, based on study compliance and adverse reactions development such as low rates of compliance, complications, or inability to tolerate the medication etc.

28.02.2025

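### The alcohol standards in sections 4.3.2, 5.4 and 7.7 do not agree, so a participant can be randomised while already meeting the AUDIT stopping criterion; the liver-enzyme criterion leaves a similar gap on one of its readings

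*Protocol*

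**What the plan says.** **Entry.** The exclusion list (section 4.3.2) deals with alcohol in one line, "History of unsafe alcohol consumption", and does not define it. Its closing item is a general discretion: "Any condition that, in the opinion of the clinician, would contraindicate the patient's participation". Neither section 4.3.1 nor 4.3.2 mentions an AUDIT score or a liver-enzyme value.

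**During the study.** Section 5.4 says that alcohol, if taken at all, "should not exceed the limit mentioned in exclusion criteria 20 g/day for women and 30g/day for men", and adds a version in units per day. The same section introduces AUDIT as a monthly assessment.

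**Stopping.** Section 7.7, under the criteria for stopping the trial or discontinuing the intervention, includes "Dosing will be stopped if liver enzymes increases > 3 x normal range" as item 1 and "Patients with AUDIT score > 8" as item 6.

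**Timing.** Table 2 (section 5.5) marks AUDIT at enrolment, allocation and every monthly visit. Liver enzymes are marked at enrolment, allocation, month 3 and month 6, and Table 1 agrees. FibroScan is done at allocation and month 6 only.

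**The concern.** A stopping criterion should describe something that happens after treatment starts, or a state that entry screening has ruled out. If the state can be present at entry and entry does not test for it, the plan allows people to be randomised who should come off treatment immediately under its own rules.

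Such stops are avoidable because the measurement is in hand before allocation. They do not favour either arm in expectation, since the state precedes randomisation. But each one takes a randomised place and yields either no month-6 result or a result after little or no treatment. There is also a population issue. The protocol studies non-alcoholic fatty liver disease, and an alcohol exclusion without a definition lets two recruiters decide differently about the same patient.

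**Working it through.** No published figure settles this point, so the check sets the sections side by side.

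**1. Alcohol standards**

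| Place | Standard | Scale |
|---|---|---|
| 4.3.2 (entry) | unsafe consumption, undefined | none |
| 5.4 (during study) | 20 g/day women, 30 g/day men, with a version in units | daily quantity |
| 7.7 (stopping) | AUDIT above 8 | questionnaire score |

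Section 5.4 says that its limit comes from the exclusion criteria, and the exclusion criteria contain no such limit. Nothing converts the daily quantity to an AUDIT score or ties either one to the word used at entry. The case report form (Annexure 1C) records alcohol under social history as none, moderate or heavy, which supplies no definition either.

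**2. Can the AUDIT criterion be met at randomisation?**
- It is a status (a score above 8), not a change from an earlier score.
- Table 2 takes the score at enrolment and again at allocation.
- No entry rule refers to the score.
- A candidate scoring above 8 whom the recruiter does not judge unsafe is therefore eligible, can be allocated, and satisfies item 6 of section 7.7 on that day.

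**3. Can the enzyme criterion be met at randomisation?**
- Sections 4.3.1 and 4.3.2 set no enzyme limit, although enzymes are measured at screening (section 4.6, Laboratory investigations; Tables 1 and 2).
- Item 1 of section 7.7 uses the normal range as its yardstick but speaks of an increase.
- *Absolute reading:* any value above 3 x normal triggers it. A candidate already above that level can be randomised while meeting it.
- *Rise reading:* a change after baseline is needed, so it cannot be met at entry.
- The text does not choose between these readings. On either one, the next scheduled liver profile after allocation is at month 3.

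**4. What happens to such a participant in the analysis (section 4.8)?**
- Leaves with no follow-up assessment: outside the modified intention-to-treat set, so sample is lost.
- Has a follow-up visit and is then lost before month 6: the last value is used. For CAP and LSM that value is the baseline scan, so the recorded change is zero.
- Stops tablets but attends month 6: an observed scan after little or no treatment, which dilutes the comparison.

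**5. Size**
The plan randomises 55 per group with a 20% dropout allowance, which is 55 x 0.20 = 11 per group. One avoidable stop is 1/55 = 1.8% of a group. The number of such stops cannot be worked out, because the protocol gives no distribution of AUDIT scores or enzyme values among candidates.

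**The case against.** The strongest reply is that entry is not unguarded. Unsafe drinking is an exclusion, AUDIT is available at enrolment to inform that judgement, a medical investigator reviews eligibility (section 4.5), and the discretionary exclusion could remove anyone about to meet a stopping criterion. This is a fair limit on the point, and it would be wrong to infer that alcohol is unrestricted at entry. But the cover is partial: nothing requires the recruiter to use the AUDIT score or the value of 8, or to exclude on enzymes.

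Some stronger readings are tempting, and the documents do not support them:

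- *That both stopping rules are plainly met at randomisation and participants are stopped at once.* This fits AUDIT. For enzymes it needs the absolute reading, and an immediate stop also needs the allocation sample to count.
- *That stopped participants become zero-change records.* This follows only for those who have a follow-up visit and are then lost before month 6. Section 7.7 stops dosing on enzymes; it does not say that follow-up ends.
- *That power falls by a stated amount.* Any share of affected participants would be invented. The answer also depends on whether they are extra losses, are absorbed by the dropout allowance, or remain as diluted observations. The sample-size section gives a difference of 3 and an SD of 5 without naming the endpoint, so a loss could not be tied to CAP, LSM or FIB-4 in any case.

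**Conclusion.** The point stands as an inconsistency in the protocol. Three alcohol standards are in use, the one governing entry has no definition, and section 5.4 cites a limit that is not where it says. As a result, a participant can be randomised while already meeting the AUDIT stopping criterion. This conclusion rests only on the protocol's text and visit schedule.

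The enzyme part is weaker. The criterion is ambiguous, and it shares the defect only if read as an absolute threshold.

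The consequence is avoidable discontinuation after randomisation, with loss of sample or dilution. Its size is unknown and may be small if recruiters apply the existing exclusions strictly. This review takes no view on which alcohol or enzyme limit is clinically right.

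**What to change.** Reconcile sections 4.3.1, 4.3.2, 5.4 and 7.7 so that the entry and stopping criteria are consistent and nobody can be randomised while already meeting a stopping criterion. Within that:

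- resolve the three alcohol standards and the undefined term in the exclusion list;
- correct the cross-reference in section 5.4, which points to a figure that the exclusion list does not contain;
- make clear in section 7.7 whether the enzyme criterion is an absolute threshold or a rise from baseline.

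The limits and the wording are for the clinical team to decide.

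The cost is protocol and case-report-form wording. AUDIT and liver enzymes are already scheduled at enrolment, so no visit or test is added. The downside is that a few screened patients may become ineligible. It is cheapest before recruitment, because section 6.2 commits the team to informing participants and taking consent again if the protocol changes during the study.

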## 4.4. Sample Size Calculation and Statistics:

#### Sample size(n)

$$n = \sigma 2(Z\alpha/2 + Z\beta)2/delta$$

where,

- $Z\alpha/2=1.96$  (for  $\alpha = 0.05$ , two-tailed test)
- $Z\beta=0.84Z$  {\beta} = 0.84 $Z\beta=0.84$  (for 80% power)
- $\sigma=5 \cdot sigma = 5\sigma=5$  (Standard Deviation)
- $\Delta=3$ \Delta =  $3\Delta=3$  (Expected Mean Difference)

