#### Calculation,

Adjusting for Dropout (20%)

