#### **Final Sample Size**

- 55 participants per group
- Total: 110 participants (both groups combined)

28.02.2025

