## 4.8. Data analysis:

Data will be analyzed using SPSS software version 21. Baseline patient characteristics will be described using descriptive statistics. Continuous variables will be expressed using mean and standard deviation or median with range depending on the distribution of data. Categorical variables will be expressed using frequency and percentage. Primary analysis will be done using a modified intention to treat (mITT) analysis where only subjects with at least one follows up assessment done will be included in the analysis.

Mean change in CAP score and LSM from baseline to 6 months will be compared between the 2 groups (Caffeine tablets vs placebo) using Independent T test or Mann Whitney U test depending on the distribution of data. For the secondary endpoints continuous variables will be compared using Independent T test or Mann Whitney U test and categorical variables will be compared using Chi square test. Repeated measures ANOVA will be used for analysis of change in variables from baseline till end of study. P value less than 0.05 will be considered statistically significant.

Safety outcomes will be described using descriptive statistics. For patients who were lost to follow up, the last available value will be used for analysis.

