## 5. Intervention, Monitoring of compliance to treatment

Caffeine tablets and placebo tablets required for the trial would be sourced from Nutricost, a U.S.-based company that specializes in high-quality dietary supplements. Nutricost products are manufactured in GMP-compliant facilities and undergo third-party testing to ensure purity and consistency. The caffeine tablets specifically contain caffeine anhydrous, a dehydrated form of caffeine that provides a standardized and effective dosage and placebo are manufactured using starch ensuring that it is inert and does not affect the study's outcomes.

The study groups will receive one bottle on the day of allocation, and it will contain either caffeine tablets or placebo required for a month. The test group will receive the caffeine tablet while the control group will receive the placebo .Tablet bottles will be issued to participants according to their random number mentioned in the Case Report Form (CRF).

Patients will be asked to take the medication every day after dinner. Recommended dose and directions for use will be given verbally when dispensing the tablet pack, and written instructions will be clearly mentioned on the label of the bottle in Sinhala, Tamil and English. The patients will be asked to take the tablets home. At each monthly visit, the participants will be asked to bring tablet bottles with balance tablets, to count at the monthly visit to assess compliance. The required tablets for next month will be issued during this visit.

Participants who have < 80% compliance will be re-educated on the importance of daily administration of investigational product, as much as possible: with the overall aim to maintain  $\ge$  80% compliance over the study period.

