## 7.7. Termination of Study and withdrawal from the study

The principal investigator will terminate a volunteer participant from the trial in the following cases. In such an event, Principal investigator will inform the participant about termination of the study and the reason for termination.

- Occurrence of an adverse event which does not justify continuation of the study
- Protocol violation which jeopardizes the performance of the study

If a volunteer is not adhering to the proposed medication protocol a detailed discussion will be held to understand the reason for non-adherence to determine whether it is tablet related or due to another reason such as forgetfulness or does not want to continue with the medication on personal preference which is unrelated to the product. No intimidation or force would be used to improve compliance if the participant refuses to provide any information

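### Section 7.7 removes or allows removal of participants from the study for treatment-related reasons, and nothing provides for their month-6 Fibroscan

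*Protocol*

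**What the plan says.** Section 7.7 contains three kinds of rule.

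- **Mandatory removal from the trial.** "The principal investigator will terminate a volunteer participant from the trial in the following cases": an adverse event that does not justify going on, or a protocol violation that jeopardises the study.
- **Dosing stops.** Under the criteria for stopping or discontinuation, items 1 to 4 (liver enzymes, conjugated bilirubin, creatinine, drug-related moderate or severe events) stop dosing. They do not mention follow-up. Items 5 and 6 are listed without saying what is stopped.
- **Discretionary withdrawal from the study.** The last paragraph of the same subsection allows the principal investigator to withdraw a patient "based on study compliance and adverse reactions development such as low rates of compliance, complications, or inability to tolerate the medication". No threshold is given.

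Other sections bear on this:

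- Section 5 handles low compliance differently: "Participants who have < 80% compliance will be re-educated on the importance of daily administration of investigational product". Section 7.7 itself also answers non-adherence with a discussion of the reasons.
- Section 4.8: "Primary analysis will be done using a modified intention to treat (mITT) analysis", defined as everyone with at least one follow-up assessment. The last available value is used for those lost to follow-up.
- Section 2.4 defines all three primary endpoints (LSM, CAP, FIB-4) as change from baseline to week 24.
- Section 4.6 (Ultrasound and Fibro scan), section 5.5 and Table 2 place Fibroscan at baseline and month 6 only. The data-collection row of the synopsis also lists it at 3 months. These places disagree.
- Section 6.1 lists palpitations, raised blood pressure, gastrointestinal discomfort, insomnia and anxiety as caffeine risks. Section 5 describes the placebo as inert starch.

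**The concern.** An intention-to-treat comparison needs the outcome from people who stop or take little of the treatment. Here the protocol can end their participation, and no sentence asks them back for the final scan. Intolerance, complications and poor compliance arise after randomisation and can be caused by the tablets, so those who lose the scan are not a random subset. Given the listed caffeine effects and an inert comparator, the two arms may well lose different numbers and different kinds of people.

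This differs from the question of how missing values are filled in, because here trial conduct creates the gap. A statistical analysis plan that is not shown could choose an imputation method, but it could not recover a scan that was never taken. The 20% dropout allowance in section 4.4 replaces lost numbers and does not correct bias.

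**Working it through.** **Inputs from the protocol.** Section 4.4: two-sided alpha 0.05, 80% power, SD 5, difference 3 (no endpoint or unit given), 20% dropout, "55 participants per group". **Assumed inputs**, because the protocol gives no rates by arm: removal of 20% on caffeine and 5% on placebo, with 30% and 10% as a wider case; a gap g of 0.5 to 1.0 SD in improvement between those kept and those removed; improvement under lifestyle advice as stated in each step.

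**1. The plan's own figure.** The standard two-sample formula gives 2 × 5² × (1.96 + 0.84)² / 3² = 43.6, so 44 per arm, and 44 / 0.80 = 55. This matches. The planned effect is 3/5 = 0.6 SD. With all 55 per arm scanned, power is 88.2%; with 44 per arm it is 80.4%.

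**2. What a removed participant contributes.** After one follow-up visit the participant is in the mITT set. Under Table 2 there is no CAP or LSM after baseline. If the last-value rule is applied, the baseline scan is carried forward and the change is 0. If it is not applied, there is no change score. Section 4.8 does not say whether investigator withdrawal counts as loss to follow-up, so both cases follow.

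**3. Observed scans only, no true effect.** If a fraction p is removed and those kept improve by g more than those removed, the mean among those kept is shifted by p × g. The difference between arms is (0.20 − 0.05) × g:
- g = 0.5: 0.075 SD, or 0.075/0.6 = 12.5% of the planned effect
- g = 1.0: 0.15 SD, or 25% of it

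Both favour caffeine. Observed numbers are 55 × 0.80 = 44 and 55 × 0.95 ≈ 52, so SE = √(1/44 + 1/52) = 0.205 SD. The standardised shifts are 0.37 and 0.73, and the nominal 5% test rejects about 6.6% and 11.3% of the time. With 30% and 10% removed, the shift is 0.20 × g = 0.10 to 0.20 SD.

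**4. Baseline carried forward, no true effect.** Both arms would improve by m, and removed participants score 0. The difference is (0.95 − 0.80) × m against caffeine. With m = 0.5 SD this is 0.075 SD. In the units of section 4.4, 55 per arm:

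| Improvement in both arms | Removed, caffeine/placebo | False difference | Two-sided rejection |
|---|---|---|---|
| 3 | 20%/5% | 0.45 against caffeine | 7.8% |
| 3 | 30%/10% | 0.60 against caffeine | 10.5% |
| 6 | 20%/5% | 0.90 against caffeine | 15.4% |
| 6 | 30%/10% | 1.20 against caffeine | 23.9% |
| 3 or 6 | 20%/20% | 0 | 5.0% |

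**5. Baseline carried forward, true difference 3.**

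| Placebo improvement | Removed, caffeine/placebo | Expected difference | Power |
|---|---|---|---|
| 0 | 20%/20% | 2.40 | 79% |
| 0 | 20%/5% | 2.40 | 75% |
| 3 | 20%/20% | 2.40 | 74% |
| 3 | 20%/5% | 1.95 | 53% |
| 3 | 30%/10% | 1.50 | 36% |

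As an example, with placebo improvement 3 and 20%/5% removed, the arm means are 0.80 × 6 = 4.80 and 0.95 × 3 = 2.85, a difference of 1.95.

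**The case against.** The strongest reply is that section 7.7 is milder than it looks, and several stronger readings do fail.

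- A reader might infer that the section equates stopping tablets with leaving the study. It does not: items 1 to 4 stop dosing only. The defect is silence about follow-up after a dosing stop, next to separate sentences that do end participation.
- A reader might infer that poor compliers or intolerant patients must be removed. That withdrawal is discretionary. Only the adverse-event and protocol-violation terminations are mandatory. Re-education, discussion and possible withdrawal could be read as escalation, so section 5 and section 7.7 need reconciling rather than being in flat contradiction.
- A reader might infer that every removal loses the whole primary outcome. FIB-4 is less affected, because its bloods are also drawn at month 3. If the synopsis is right about a 3-month Fibroscan, later removals would also leave an interim CAP and LSM. The week-24 values would still be missing.
- A reader might infer that the analysis becomes tolerant caffeine users against nearly all placebo users. That describes an observed-case analysis. Section 4.8 keeps anyone with a follow-up visit in the mITT set and has a last-value rule.
- A reader might infer a known bias in favour of caffeine. No rates by arm are given, nothing shows that intolerant patients improve less, and the sign reverses under carry-forward.

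What remains is that no sentence keeps these participants in follow-up. The loss of their scan is inferred from that absence; the protocol does not state that the scan is omitted.

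**Conclusion.** The point holds in this form. Following section 7.7 as written can lose week-24 CAP and LSM, two of the three primary endpoints, for reasons related to treatment and adherence. This weakens the mITT comparison whether the missing scans are excluded or replaced by baseline. Unequal loss between arms is plausible from the protocol's own account of caffeine effects and an inert placebo, but it is not established.

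The size is illustrative. At 20% against 5% removal the error is of the order of 0.1 SD against a planned 0.6 SD, and its direction depends on how the missing scans are handled. Larger imbalance, or larger improvement in both arms, makes it worse. The documents do not support a firmer figure or a predicted direction.

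**What to change.** Leave the dosing-stop criteria and the investigator's safety discretion as they are. Then:

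1. In section 7.7, define discontinuation of study tablets and withdrawal from the study as separate events, and say which of the two each listed criterion triggers.
2. State that participants whose tablets are stopped, or who comply poorly, are asked to attend the remaining visits, or at least the month-6 Fibroscan and bloods, unless they withdraw consent or attendance is judged unsafe.
3. Reconcile the section 7.7 wording on termination and on withdrawal for low compliance or intolerance with the re-education rule in section 5 and the mITT analysis in section 4.8.
4. Reconcile the Fibroscan timing in the synopsis with sections 4.6 and 5.5 and Table 2.
5. Record the tablet-stop date and the study-exit date in separate CRF fields.

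The cost is protocol wording and two CRF fields. A few participants who are off tablets would attend visits and scans already planned for them. The change has to be in place before the month-6 visits, because missed scans cannot be recovered.
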